## 2.2. Study Objective(s) and Endpoint(s)

Objectives	Endpoints
Primary Objectives	Primary Endpoints

 
To assess the safety and tolerability of single (fed and fasted) and repeat doses of GSK2983559 in healthy participants.
 
	
 
Safety and tolerability of GSK2983559 as assessed by clinical monitoring and reporting of adverse events and serious adverse events, change in laboratory values, ECG, vital signs, physical examinations.
 

Secondary Objectives	Secondary Endpoints

 
To characterise the PK profile of single (fasted) doses of GSK2983559 and its active moiety GSK2668176 in healthy participants.
 
	
 
Derived PK parameters for GSK2983559 and GSK2668176 including area under the plasma drug concentration versus time curve (<math>AUC_{(0-t)}</math>, <math>AUC_{(0-\infty)}</math>), maximum observed plasma drug concentration (<math>C_{max}</math>), time to maximum observed plasma drug concentration (<math>t_{max}</math>), and terminal half-life (<math>t_{1/2}</math>) following single (fasted) doses, where data allow.
 

 
To characterise the PK profile of repeat doses of GSK2983559 and its active
 
	
 
Derived PK parameters for GSK2983559 and GSK2668176 including area under the plasma drug concentration versus time curve (<math>AUC_{(0-t)}</math>,
 

Objectives	Endpoints

moiety GSK2668176 in healthy participants.
	
AUC(0-t), maximum observed plasma drug concentration (Cmax), time to maximum observed plasma drug concentration (tmax), and terminal half-life (t1/2) following single and repeat doses, and estimation of an accumulation ratio where data allow.


 
To assess the effect of food on the pharmacokinetics of GSK2983559 and its active moiety GSK2668176 in fasted and fed state in healthy participants.
 
	
 
Derived PK parameters for GSK2983559, and GSK2668176 including area under the plasma drug concentration versus time curve (AUC(0-t), AUC(0-∞)), maximum observed plasma drug concentration (Cmax), time to maximum observed plasma drug concentration (tmax), and terminal half-life (t1/2) following single (fed and fasted) dose, where data allow.
 

Exploratory Objectives	Exploratory Endpoints

 
To determine the PD effect of single and repeat doses of GSK2983559 in healthy participants.
 
	
 
PD/biomarker endpoints may include, but not be limited to, assessments of pharmacologic effects through measurements of target engagement and pathway activation. These may include measurements of RIP-2 receptor occupancy, and levels of MIP1<math>\alpha</math>, MIP1<math>\beta</math> and TNF proteins, following stimulation of whole blood, as data permit. (Cohort 1 subjects only)
 

 
To investigate the metabolic profile of GSK2983559 following single and/or repeat doses in healthy participants in blood and urine
 
	
 
Identification and quantitative estimates of GSK2983559 and its active moiety GSK2668176 and potential metabolites following single and repeat doses in plasma and urine.
 

 
To characterize exposure to 5-ABT and NAc-5-ABT after single and repeated doses of GSK2983559 in healthy participants.
 
	
 
Concentration of 5-ABT and NAc-5-ABT (adjusted to 5-ABT concentration based on molecular weight (MW)) and derive Cmax for the combined concentration curve of 5-ABT and MW adjusted NAc-5-ABT
 

### 2.3. Study Design

Overview of Study Design and Key Features – Part A Single Ascending Dose	
Design Features	
 
• Separate participants will be enrolled into both cohorts of Part A.
 
• Cohort 1 Standard Capsule: 5-way crossover design. Each participant will receive single ascending oral doses of either GSK2983559 or placebo in a 4:1 ratio according to the randomisation schedule, in study periods 1 to 5, in a blinded manner.
 
• Cohort 2 Enteric Capsule: 4-way crossover design for single ascending dose, including an additional period for assessing GSK2983559 under fed conditions (period 5 – open-label).
 
• During the blinded part, each participant will receive single ascending oral doses of either GSK2983559 or placebo in a 3:1 ratio according to the randomisation schedule, in study periods 1 to 4, in a blinded manner.
 
• Cohorts 1 and 2 will be dosed sequentially, incorporating sentinel participants: Cohort 1 will complete all 5 dosing periods before Cohort 2 begins.
 
• Following completion of Cohort 1 and before starting Cohort 2, a GSK internal safety board (independent of DEC) will be reviewing the data.
 
• Based on emerging PK data, all doses may not be investigated.
 
• There will be a at least 48-hour washout period between each dose escalation step but the washout period may be extended depending on emerging data.
 

Dosing	
 
• Participants will be randomised on Day 1 followed by a single oral dose of GSK2983559
 
• Sentinel dosing will be employed within each ascending dose cohort and treatment period (except for when investigating the food effect).
 
• On Day 1, one participant will receive GSK2983559 and one participant will receive matched-placebo, to evaluate tolerability and safety for at least 24 hours post-dose.
 
• Dosing in the remaining 8 and 10 participants in Cohorts 1 and 2, and treatment period will occur at least 24 hours later after review of safety results from the initial
 

Overview of Study Design and Key Features – Part A Single Ascending Dose							
	2 participants in a 7:1 and 4:1 ratios (GSK2983559: placebo) for Cohorts 1 and 2, respectively						
Time & Events	
 
Refer to Appendix 2: Schedule of Activities
 
						
Treatment Assignment	
 
At screening a unique number (case report form [CRF] number) will be assigned to any participant who has at least one Screening procedure performed, other than signed informed consent. The unique number will be used to identify individual participants during the course of the study.
 
Participants who meet the screening eligibility criteria will be randomised to a treatment group through an Interactive Response Technology (IRT). The IRT will confirm the participants CRF number and provide the randomisation number, where, a randomisation number will be assigned from a randomisation schedule generated by Clinical Statistics, prior to the start of the study, using validated internal software. Once assigned, this number must not be reassigned to any other participant in the study.
 
The randomisation is centrally controlled by the IRT.
 
 
Part A
 
Within Cohort 1, participants will be assigned to one of 5 dosing sequences in a 1:1:1:1:1 ratio.
 
Within Cohort 2, participants will be assigned to one of up to 4 dosing sequences in a 1:1:1:1 ratio.
 
  
 	Cohort 1	Cohort 2	
   
 Sequence	PBCDE APCDE ABPDE ABCPE ABCDP	PGHIJ FPHIJ FGPIJ FGHPJ	
  
 
Participants will be randomised to:
		Cohort 1	Cohort 2	Sequence	PBCDE APCDE ABPDE ABCPE ABCDP	PGHIJ FPHIJ FGPIJ FGHPJ
	Cohort 1	Cohort 2					
Sequence	PBCDE APCDE ABPDE ABCPE ABCDP	PGHIJ FPHIJ FGPIJ FGHPJ					

Overview of Study Design and Key Features – Part A Single Ascending Dose																																						
	
  
 Treatment code	Original Planned Treatment Description	Cohort 1 Actual Treatment & Cohort 2 Planned Treatment Description	
   
 A	2 mg GSK2983559		
 
 B	10 mg GSK2983559	4 mg GSK2983559	
 
 C	30 mg GSK2983559	10 mg GSK2983559	
 
 D	75 mg GSK2983559	30 mg GSK2983559	
 
 E	150 mg GSK2983559	100 mg GSK2983599	
 
 F	300 mg GSK2983559	200 mg GSK2983599	
 
 G	600 mg GSK2983559	400 mg GSK2983559	
 
 H	800 mg GSK2983559	600 mg GSK2983559	
 
 I	Dose TBC GSK2983559	Dose TBC GSK2983559	
 
 J	GSK2983559 Fed	GSK2983559 Fed	
 
 P	Placebo		
  
	Treatment code	Original Planned Treatment Description	Cohort 1 Actual Treatment & Cohort 2 Planned Treatment Description	A	2 mg GSK2983559		B	10 mg GSK2983559	4 mg GSK2983559	C	30 mg GSK2983559	10 mg GSK2983559	D	75 mg GSK2983559	30 mg GSK2983559	E	150 mg GSK2983559	100 mg GSK2983599	F	300 mg GSK2983559	200 mg GSK2983599	G	600 mg GSK2983559	400 mg GSK2983559	H	800 mg GSK2983559	600 mg GSK2983559	I	Dose TBC GSK2983559	Dose TBC GSK2983559	J	GSK2983559 Fed	GSK2983559 Fed	P	Placebo		
Treatment code	Original Planned Treatment Description	Cohort 1 Actual Treatment & Cohort 2 Planned Treatment Description																																				
A	2 mg GSK2983559																																					
B	10 mg GSK2983559	4 mg GSK2983559																																				
C	30 mg GSK2983559	10 mg GSK2983559																																				
D	75 mg GSK2983559	30 mg GSK2983559																																				
E	150 mg GSK2983559	100 mg GSK2983599																																				
F	300 mg GSK2983559	200 mg GSK2983599																																				
G	600 mg GSK2983559	400 mg GSK2983559																																				
H	800 mg GSK2983559	600 mg GSK2983559																																				
I	Dose TBC GSK2983559	Dose TBC GSK2983559																																				
J	GSK2983559 Fed	GSK2983559 Fed																																				
P	Placebo																																					
Interim Analysis	
 
No Interim Analysis were conducted due to study termination
 
																																					

Overview of Study Design and Key Features – Part B Multiple Ascending Dose													
	
 
Study terminated prior to Part B start, please refer to protocol for exact details
 
												
Treatment Assignment	
 
Part B treatment codes were planned to be:
 
 
  
 Treatment code	Treatment Description	
   
 K	Dose 1 GSK2983559	
 
 L	Dose 2 GSK2983559	
 
 M	Dose 3 GSK2983559	
 
 N	Dose 4 GSK2983559	
 
 P	Placebo	
  
	Treatment code	Treatment Description	K	Dose 1 GSK2983559	L	Dose 2 GSK2983559	M	Dose 3 GSK2983559	N	Dose 4 GSK2983559	P	Placebo
Treatment code	Treatment Description												
K	Dose 1 GSK2983559												
L	Dose 2 GSK2983559												
M	Dose 3 GSK2983559												
N	Dose 4 GSK2983559												
P	Placebo												

## 2.4. Statistical Hypotheses / Statistical Analyses

The objectives of this study are to assess the safety and tolerability of single and repeat ascending doses of GSK2983559 in healthy volunteers. No formal hypotheses will be tested.

### **3. PLANNED ANALYSES**

#### **3.1. Interim Analyses**

Dose escalation meetings occurred after each period in Part A and were scheduled to occur following the completion of 14 days dosing of each cohort in Part B. The decision to proceed to the next cohort and next dose strength to be studied, was made by the Dose Escalation Committee (DEC) based on assessment of blinded safety (e.g., AEs, clinical laboratory results, vital signs and ECG), active moiety (GSK2668176) pharmacokinetic and 5-ABT concentrations obtained in all participants at the prior dose level. Individual safety data (adverse events, laboratory safety tests, ECGs and vital signs) was reviewed. This study was double blind (sponsor open), where the participant, investigator and site staff will remain blinded to the treatment allocation. Sponsor open refers only to those members of the DEC as required.

Following completion of Cohort 1: Part A and before starting Cohort 2: Part A, a GSK internal safety board (independent of DEC) reviewed the emerging PK and safety data.

A formal interim analysis was due to be performed during the study on completed cohorts in Part A of the study to aid internal decision making only. The study was terminated prior to completion of Part A.

#### **3.2. Final Analyses**

The final planned primary analyses will be performed after the completion of the following sequential steps:

All participants have completed the study as defined in the protocol or the study is terminated.

All required database cleaning activities have been completed and final database release (DBR) and database freeze (DBF) has been declared by Data Management.

All criteria for unblinding the randomisation codes have been met.

Randomisation codes have been distributed according to RandAll NG procedures.

## 4. ANALYSIS POPULATIONS

Population	Definition / Criteria	Analyses Evaluated
Screened	All participants who were screened for eligibility	Screen Failure Population Analysed.
Randomised	All participants who were randomly assigned to treatment in the study. This population will be based on the treatment the participant was randomised to.	Age ranges
Safety	All randomised participants who received at least one dose of study treatment. This population will be based on the treatment the subject actually received. Note: Participants who were not randomised but received at least one dose of study treatment should be listed.	All other Study Population Safety
Pharmacokinetic (PK)	All participants in the Safety population who had at least 1 non-missing PK assessment (Non-quantifiable [NQ] values will be considered as non-missing values). This population will be based on the treatment the participant actually received.	PK

Refer to [Appendix 10: List of Data Displays](#) which details the population used for each display.

### 4.1. Protocol Deviations

Important protocol deviations (including deviations related to study inclusion/exclusion criteria, conduct of the trial, patient management or patient assessment) will be summarised and listed.

Protocol deviations will be tracked by the study team throughout the conduct of the study in accordance with the Protocol Deviation Management Plan Version 2 (08-Feb-2018).

- Data will be reviewed prior to unblinding and freezing the database to ensure all important deviations are captured and categorised on the protocol deviations dataset.
- This dataset will be the basis for the summaries and listings of protocol deviations.

A separate summary and listing of all inclusion/exclusion criteria deviations will also be provided. This summary will be based on data as recorded on the inclusion/exclusion page of the eCRF.

## 5. CONSIDERATIONS FOR DATA ANALYSES AND DATA HANDLING CONVENTIONS

### 5.1. Study Treatment & Sub-group Display Descriptors

Treatment Group Descriptions			
RandAll NG		Data Displays for Reporting	
Code	Description	Description	Order in TLF
A	GSK2983559 single dose 1	GSK 2 mg	2
B	GSK2983559 single dose 2	GSK 4 mg	3
C	GSK2983559 single dose 3	GSK 10 mg	4
D	GSK2983559 single dose 4	GSK 30 mg	5
E	GSK2983559 single dose 5	GSK 100 mg	6
F	GSK2983559 single dose 6	GSK 200 mg E	7
G	GSK2983559 single dose 7	GSK 400 mg E	8
H	GSK2983559 single dose 8	GSK XX mg E 	Not used
I	GSK2983559 single dose 9	GSK XX mg E 	Not used
J	GSK2983559 fed single dose	Not Used	Not used
P	Placebo single dose	Placebo	1
K	GSK2983559 repeat dose 1	Not Used	Not used
L	GSK2983559 repeat dose 2	Not Used	Not used
M	GSK2983559 repeat dose 3	Not Used	Not used
N	GSK2983559 repeat dose 4	Not Used	Not used
Q	Placebo repeat dose	Not Used	Not used

1. Dose level not required as the study was terminated prior to being utilised

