## 5. STUDY DESIGN

### 5.1. Overall Design

[figure not shown]
This study will be a randomised, double-blind (sponsor open), placebo-controlled, two-part study of oral administration of GSK2983559 in healthy participants. Part A will be a single ascending dose crossover design in two separate cohorts of participants (Cohorts 1 and 2). In addition to the crossover treatment periods, subjects in Cohort 2 will participate in an additional treatment period and receive open-label GSK2983559 under fed conditions. Part B will be a repeat dose design in up to 4 cohorts of participants (Cohorts 3-6). This study is planned to include approximately 62 participants.

Parts A and B of this study will be double-blind with respect to participants, investigator and site staff (with the exception of the site pharmacist). Sponsor open refers only to members of the Dose Escalation Committee (DEC) at defined meetings. Members and requirements are provided in a Dose Escalation Charter.

- **Part A** – single ascending doses, randomized, placebo controlled, crossover.

Part A plans to explore up to 9 single ascending dose levels. This will be 2 cohorts, Cohort 1 (standard capsule) and Cohort 2 (enteric capsule), of 10 and 12 healthy participants, respectively. The total duration of Part A of the study for each participant, including screening and follow-up, is approximately 11 weeks.

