## 7.1. Treatments Administered

Product name:	GSK2983559	Placebo	GSK2983559	Placebo
Formulation description:	API filled capsule	Avicel filled capsule	API filled capsule	Avicel filled capsule
Dosage form:	HPMC Capsule	HPMC Capsule	HPMC Capsule	HPMC Capsule
Unit dose strength(s)/Dosage level(s):	2-45 mg	NA	100, 114 mg	NA
Route/ Administration/ Duration:	Oral	Oral	Oral	Oral
Dosing instructions:	Dose with water	Dose with water	Dose with water	Dose with water
Physical description:	Size 0 Swedish Orange capsule containing white to almost white solid	Size 0 Swedish Orange capsule containing white to almost white solid	Size 00 White Opaque capsule containing white to almost white solid	Size 00 White Opaque capsule containing white to almost white solid
Manufacturer/ source of procurement:	GlaxoSmithKline	GlaxoSmithKline	GlaxoSmithKline	GlaxoSmithKline
Method for individualizing dosage:	Site to assemble	Site to assemble	Site to assemble	Site to assemble

HPMC – Hydroxypropylmethyl Cellulose

Product name:	GSK2983559	Placebo
Formulation description:	API filled capsule	Avicel filled capsule
Dosage form:	HPMCAS Capsule	HPMCAS Capsule
Unit dose strength(s)/Dosage level(s):	50-100 mg	NA
Route/ Administration/ Duration:	Oral	Oral
Dosing instructions:	Dose with water	Dose with water
Physical description:	Size 00 White Opaque capsule containing white to almost white solid	Size 00 White Opaque capsule containing white to almost white solid
Manufacturer/ source of procurement:	GlaxoSmithKline	GlaxoSmithKline
Method for individualizing dosage:	Site to assemble	Site to assemble

HPMCAS – Hydroxypropylmethyl Cellulose Acetate Succinate

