#### Part A

Within Cohort 1, participants will be assigned to one of 5 dosing sequences in a 1:1:1:1:1 ratio.

Within Cohort 2, participants will be assigned to one of up to 4 dosing sequences in a 1:1:1:1 ratio.

Participants will be randomised to:

	Cohort 1	Cohort 2
Sequence	PBCDE APCDE ABPDE ABCPE ABCDP	PGHIJ FPHIJ FGPIJ FGHPJ

Where the treatment codes are as follows:

Treatment code	Original Planned Treatment Description	Cohort 1 Actual Treatment & Cohort 2 Planned Treatment Description
A	2 mg GSK2983559	
B	10 mg GSK2983559	4 mg GSK2983559
C	30 mg GSK2983559	10 mg GSK2983559
D	75 mg GSK2983559	30 mg GSK2983559
E	150 mg GSK2983559	100 mg GSK2983599
F	300 mg GSK2983559	200 mg GSK2983599
G	600 mg GSK2983559	400 mg GSK2983559
H	800 mg GSK2983559	600 mg GSK2983559
I	Dose TBC GSK2983559	Dose TBC GSK2983559
J	GSK2983559 Fed	GSK2983559 Fed
P	Placebo	

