## 2. SUMMARY OF KEY PROTOCOL INFORMATION

### 2.1. Changes to the Protocol Defined Statistical Analysis Plan

This study was terminated during Cohort 2 of Part A. Participants in Cohort 2 received only 2 of 4 planned single doses.

Changes from the originally planned statistical analysis specified in the protocol are outlined in [Table 1](#).

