## 11.10.4. Study Population Tables

Study Population Tables					
No.	Population	IDSL / Example Shell	Title	Programming Notes	Deliverable [Priority]
Subject Disposition					
1.1.	Safety	ES8A	Summary of Subject Status and Reason for Study Withdrawal: Part A	ICH E3, FDAAA, EudraCT  Add footnote: Note: "Subjects" is used to refer to "Participants" in all data displays to reflect GSK display standards and CDISC SDTM/ADaM standards.	SAC
1.2.	Safety	ES4	Summary of Subject Disposition at Each Study Epoch: Part A	ICH E3 Page by cohort, include treatment column for Randomised Trt Sequence and Total Column	SAC
1.3.	Screened	ES6	Summary of Screening Status and Reasons for Screen Failure: Part A	Journal Requirements	SAC
Protocol Deviation					
1.4.	Safety	DV1	Summary of Important Protocol Deviations: Part A	ICH E3	SAC

Study Population Tables					
No.	Population	IDSL / Example Shell	Title	Programming Notes	Deliverable [Priority]
Population Analysed					
1.5.	All Subjects	SP1	Summary of Study Populations: Part A	IDSL Add the following footnotes: [1] Subjects are included in the Randomised population if they were randomly assigned to treatment in the study. [2] Subjects are included in the Safety population if they have been randomised and received at least one dose of study treatment. [3] Subjects are included in the Pharmacokinetic population if they are in the Safety Population and a pharmacokinetic sample was obtained and analysed.	SAC
Demographic and Baseline Characteristics					
1.6.	Safety	DM1	Summary of Demographic Characteristics: Part A	ICH E3, FDAAA, EudraCT Overall and by cohort Include treatment column for randomised treatment sequence and total column	SAC

Study Population Tables					
No.	Population	IDSL / Example Shell	Title	Programming Notes	Deliverable [Priority]
1.7.	Randomised	DM11	Summary of Age Ranges: Part A	EudraCT Only include age ranges applicable to the study ('Adult (18-64 years)' and '>=65-84 years') Please add footnote to say that randomised population=enrolled population. Overall and by cohort Include treatment column for randomised treatment sequence and total column	SAC
1.8.	Safety	DM5	Summary of Race and Racial Combinations: Part A	ICH E3, FDA, FDA, EudraCT Overall and by cohort Include treatment column for randomised treatment sequence and total column	SAC
Prior and Concomitant Medications					

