## 11.10.5. Safety Tables

Safety: Tables					
No.	Population	IDSL / Example Shell	Title	Programming Notes	Deliverable [Priority]
Adverse Events (AEs)					
3.1.	Safety	AE1CP	Summary of All Adverse Events by System Organ Class and Preferred Term: Part A	ICH E3	SAC
3.2.	Safety	AE5A	Summary of All Adverse Events by Maximum Grade / Intensity by System Organ Class and Preferred Term: Part A	ICH E3	SAC
3.3.	Safety	AE5A	Summary of All Drug-Related Adverse Events by System Organ Class and Preferred Term and Maximum Intensity: Part A	ICH E3	SAC
3.4.	Safety	AE15	Summary of Common ( $\geq 10\%$ ) Non-serious Adverse Events by System Organ Class and Preferred Term (Number of Participant and Occurrences) : Part A	FDAAA, EudraCT	SAC
Serious and Other Significant Adverse Events					
3.5.	Safety	AE16	Summary of Serious Adverse Events by System Organ Class and Preferred Term (Number of Subjects and Occurrences) : Part A	FDAAA, EudraCT	SAC
3.6.	Safety	AE3	Summary of Adverse Events Leading to Permanent Discontinuation of Study Treatment or Withdrawal from Study by System Organ Class and Preferred Term /by Overall Frequency: Part A	IDSL	SAC
Laboratory: Chemistry					
3.7.	Safety	LB1	Summary of Chemistry Changes from Baseline: Part A	ICH E3	SAC

Safety: Tables					
No.	Population	IDSL / Example Shell	Title	Programming Notes	Deliverable [Priority]
3.8.	Safety	LB17	Summary of Worst Case Chemistry Results by PCI Criteria Post-Baseline Relative to Baseline: Part A	ICH E3	SAC
Laboratory: Hematology					
3.9.	Safety	LB1	Summary of Hematology Changes from Baseline: Part A	ICH E3	SAC
3.10.	Safety	LB17	Summary of Worst Case Hematology Results by PCI Criteria Post-Baseline Relative to Baseline: Part A	ICH E3	SAC
Laboratory: Urinalysis					
3.11.	Safety	LB1	Summary of Urine Concentration Changes from Baseline: Part A	ICH E3	SAC
3.12.	Safety	UR1	Summary of Worst Case Urinalysis Results (Discrete or Character Values) Post-Baseline Relative to Baseline: Part A	ICH E3	
Laboratory: Hepatobiliary (Liver)					
3.13.	Safety	LIVER1	Summary of Liver Monitoring/Stopping Event Reporting: Part A	IDSL	SAC
3.14.	Safety	LIVER10	Summary of Hepatobiliary Laboratory Abnormalities: Part A	IDSL	SAC
ECG					
3.15.	Safety	EG1	Summary of ECG Findings : Part A	IDSL	SAC
3.16.	Safety	EG10	Summary of Maximum QTc Values Post-Baseline Relative to Baseline by Category: Part A	IDSL	SAC

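### The SAP shows single-dose placebo as one pooled column, so the safety displays for 200 mg E and 400 mg E do not show their concurrent enteric-capsule control

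*SAP*

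**What the plan says.** SAP 5.1 lists the reporting columns. Codes F and G appear as GSK 200 mg E and GSK 400 mg E, apart from the standard-capsule doses. Code P, described as "Placebo single dose", has one display label (Placebo) and one display position, with no enteric counterpart. SAP 5.4 names no strata or subgroups, and the SAP gives no reason for pooling placebo.

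The protocol keeps the two placebo groups apart in four ways:

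- **Capsule.** Protocol 5.1 describes "Cohort 1 (standard capsule) and Cohort 2 (enteric capsule), of 10 and 12 healthy participants, respectively". Protocol 7.1 lists placebo in an HPMC capsule and, in a separate table, placebo in an "HPMCAS Capsule".
- **Randomisation.** Protocol 7.3 (Part A) states "Within Cohort 1, participants will be assigned to one of 5 dosing sequences in a 1:1:1:1:1 ratio" and "Within Cohort 2, participants will be assigned to one of up to 4 dosing sequences in a 1:1:1:1 ratio".
- **People.** Protocol 5.1 enrols separate participants in the two cohorts.
- **Time.** Protocol 5.1 has Cohort 1 finish all five periods before Cohort 2 starts.

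SAP 2.1 reports that the study stopped early: "Participants in Cohort 2 received only 2 of 4 planned single doses".

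SAP 11.10.4 asks for demographics, age and race (Tables 1.6 to 1.8) "Overall and by cohort", and Table 1.2 is paged by cohort. SAP 11.10.5 makes no such request for any safety table, from Table 3.1 ("Summary of All Adverse Events by System Organ Class and Preferred Term: Part A") to Table 3.22. Nor does SAP 11.10.6 for Figure 3.1, the plot of common adverse events with relative risk.

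**The concern.** Safety is the primary objective, and 200 mg E and 400 mg E are the two highest doses given. Their only control that is randomised with them, concurrent with them and in the same capsule is Cohort 2 placebo. In the planned columns that group is merged with a larger group from an earlier cohort in a different capsule.

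If the background rate of an event differs between cohorts, through the people, the calendar time or the capsule, the pooled column moves away from the right reference for the enteric doses. An inert dose could then look harmful, or a real effect could be masked. The same happens, to a lesser degree, to the Cohort 1 doses, whose control column includes enteric placebo.

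The point concerns the safety summaries only. Placebo is not an issue for the PK summaries, and the PD summaries cover Cohort 1 alone (SAP 9.1.1).

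**Working it through.** **1. Reproduce the plan's allocation.** Protocol 5.2 gives 8 on active of 10 in Cohort 1 and 9 on active of 12 in Cohort 2. From the ratios in Protocol 5.1 (4:1 and 3:1):

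- Cohort 1: 10 × 4/5 = 8 active, so 2 on placebo per period.
- Cohort 2: 12 × 3/4 = 9 active, so 3 on placebo per period.

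The sentinel rule agrees: 1 + 7 = 8 active and 1 + 1 = 2 placebo in Cohort 1; 1 + 8 = 9 active and 1 + 2 = 3 placebo in Cohort 2.

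**2. Count the placebo exposures.** Each sequence has one blinded placebo period, so exposures and participants coincide.

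- Cohort 1, five periods: 2 × 5 = 10.
- Cohort 2, the two periods given: 3 × 2 = 6.
- Pooled column: 10 + 6 = 16.
- Share that is non-concurrent, standard-capsule placebo for the enteric doses: 10/16 = 62.5%.
- Share that is enteric placebo for the Cohort 1 doses: 6/16 = 37.5%.

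**3. Vary the count.** The documents do not give the numbers actually dosed in Cohort 2.

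| Cohort 2 placebo exposures | Share standard capsule |
|---|---|
| 6: both periods full, 12 participants | 10/16 = 62.5% |
| 4: period 1 full, only the sentinel on placebo in period 2 | 10/14 = 71% |
| 4: Cohort 2 with the 8 participants still stated in Protocol 11.1 | 10/14 = 71% |
| 3: period 1 only | 10/13 = 77% |
| 12: all four planned periods, had they been run | 10/22 = 45% |

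Shortfalls raise the share. Early termination is what made the standard capsule the majority.

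**4. Size of a possible error.** Let p_S and p_E be the placebo event rates in Cohorts 1 and 2. The pooled rate is (10 p_S + 6 p_E)/16, so it differs from p_E by 0.625 × (p_S − p_E). The rates below are assumptions, since the documents give none. The enteric dose is taken to have no effect, so its rate is p_E.

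- p_S = p_E: no error; apparent relative risk 1.0.
- p_S = 10%, p_E = 30%: pooled (1 + 1.8)/16 = 17.5%; apparent relative risk 0.30/0.175 = 1.71.
- p_S = 30%, p_E = 10%: pooled (3 + 0.6)/16 = 22.5%; apparent relative risk 0.10/0.225 = 0.44.

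**5. Precision given up by splitting.** With 0 events in n, the exact two-sided 95% upper limit is 1 − 0.025^(1/n): 45.9% for n = 6 and 20.6% for n = 16.

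**6. Bias and precision together.** Root-mean-square error as an estimate of p_E:

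- Pooled: √{[0.625 (p_S − p_E)]² + [10 p_S(1 − p_S) + 6 p_E(1 − p_E)]/256}
- Placebo E alone: √{p_E(1 − p_E)/6}

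| p_S, p_E (assumed) | Pooled | Placebo E alone |
|---|---|---|
| 20%, 20% | 0.100 | 0.163 |
| 10%, 30% | 0.155 | 0.187 |
| 30%, 10% | 0.161 | 0.122 |

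Neither column is better throughout, which is the reason to show both.

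**The case against.** **The analysis is descriptive.** No hypotheses are tested (SAP 2.4), and no model or rule compares an enteric dose with placebo. That stands: no error rate is affected. Descriptive tables are still read by setting dose columns beside placebo. Figure 3.1 shows relative risk, and if its reference is placebo, the pooled rate is the denominator. The SAP does not state the reference.

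**The safety tables may already be split.** They point to standard shells that are not in the documents, so a split inside a shell cannot be ruled out. What can be said is that the SAP specifies none for safety and does specify one elsewhere.

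**Laboratory, ECG and vital-sign differences largely cancel.** Baseline is reset in each Part A period (SAP 5.2), and the main summaries are of change from baseline. Stable level differences between cohorts therefore mostly drop out. This stands, and it limits the concern to adverse event counts and to differences in within-period change.

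**A cohort difference is speculative.** Both placebos are Avicel-filled, one HPMC placebo has the same size and colour as the HPMCAS one, and the site, eligibility criteria and Part A schedule are common. The documents report no difference in placebo event rates. This is fair, and it is why the result is conditional.

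**The protocol uses one code.** Protocol 7.3 has P for placebo in both cohorts, so the SAP follows the protocol's coding. That explains the single column but is not a reason for pooling. The SAP does give Part B placebo its own code, Q.

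**The data remain traceable.** The listings of all adverse events and of planned and actual treatments allow reconstruction by participant, but that does not replace a summary.

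**Pooling buys precision.** It does, as steps 5 and 6 show. A reader might infer that statements on 200 mg E and 400 mg E should rest on Placebo E alone. The numbers do not support that: with about 6 participants it exchanges a possible bias for a certain loss of precision, and under one of the two assumed unequal-rate scenarios pooled placebo is the closer estimate.

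**Conclusion.** The point holds as a matter of display. The single Placebo column merges two groups that differ in capsule, randomisation, people and time. On the planned allocation, 62.5% of it is non-concurrent standard-capsule placebo, so the specified safety summaries do not show the concurrent randomised control for the two enteric doses. The figure assumes 12 participants in Cohort 2, both periods fully dosed and no replacements; the shortfalls considered put it at 71% to 77%.

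A reader might go further and conclude that the safety findings for 200 mg E and 400 mg E are biased. The documents do not support that. Bias needs placebo event rates or within-period changes that differ between cohorts, and nothing in the documents shows that they do. The relative risks of 1.71 and 0.44 come from assumed rates and show how the error would work, not how large it is.

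This is a cheap improvement to a descriptive report and does not invalidate the plan.

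**What to change.** In SAP 5.1, keep code P but split it for display into Placebo (Cohort 1, standard capsule) and Placebo E (Cohort 2, enteric capsule). Show both beside the pooled placebo column in the safety summaries, above all the adverse event tables and Figure 3.1, and state in Figure 3.1 which group is the reference. Read 200 mg E and 400 mg E against both Placebo E and pooled placebo, and do not require conclusions to rest on Placebo E alone.

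The change needs no new data. It costs one more label and column, and that column is small (about 6 participants) and imprecise. A footnote giving its size would guard against over-reading it.
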